6.1.1. Pseudo Code

The following SAS® pseudo code will be used to calculate the following:

Chi-Square test at 5% two-sided significance level and odds ratio (and 95% asymptotic CI):

```
proc freq;
  Table treatment*analysis_variable / chisq;
  ods output ChiSq=outputdsn1;
  ods output RelativeRisks=outputdsn2;
run;
```

Fisher's Exact test at 5% two-sided significance level:

```
proc freq;
  Table treatment*analysis_variable / exact;
  ods output FishersExact=outputdsn;
run;
```

95% Wilson CI for proportions/percentages:

```
proc freq;
  Table treatment*analysisvariable / binomial(wilson);
  ods output binomialcls=outputdsn;
run;
```

95% Wilson CI for difference in proportions (produces Newcombe CI):

```
proc freq;
  Table treatment*analysisvariable / riskdiff(cl=Wilson);
  Exact Riskdiff;
  ods output pdiffcls=outputdsn;
run;
```

6.2. Timing of Analyses

The interim analysis will be conducted when approximately half (n=123) of subjects have contributed primary outcome measure data.

The final analysis will be performed after database lock when all subjects have been followed through Visit 3, the final study visit, at Day 29 (Window: Day 25-31).

6.3. Analysis Populations

6.3.1. Safety Analyses

All Safety analyses will be performed in the safety analysis population. The safety population includes all randomized subjects who receive at least one dose of study drug.

6.3.2. Efficacy Analyses

6.3.2.1. Intent-to-Treat Analysis (ITT) Population

The Intent-to-Treat (ITT) population includes all randomized subjects, regardless of whether they received study treatment, had a positive baseline rectal CT NAAT result, or were compliant with the administration procedures or schedule.

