5.1 Subject Inclusion Criteria

Subjects eligible to enroll in this trial must meet all inclusion criteria:

1. Willing and able to understand and provide written informed consent before initiation of any study procedures
2. Willing and able to comply with planned study procedures for all study visits
3. Male sex at birth and aged ≥ 18 years with valid contact information
4. At least one male sex partner (oral or anal) in the past 12 months
5. Untreated rectal CT diagnosed by a positive NAAT result
6. Willingness to abstain from condomless receptive anal sex during the trial
7. Willingness to complete a 7-day study drug regimen

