7.1 Visit 0 – Screening Visit (Day -30 to -1)

- Sites will follow their site-specific instructions for approaching and pre-screening potential subjects for the screening visit. Potential subjects aged ≥ 18 years seeking care in participating clinics will be pre-screened for preliminary study eligibility if they are considered high risk for rectal chlamydia and have not taken antibiotics in the past 21 days. High risk is defined as a) having known contact to chlamydia and receptive anal intercourse in the past 30 days or b) identified by a clinician as having an indication for empiric treatment.
- Potential subjects who meet these criteria will be provided with a description of the trial (purpose and study procedures) and asked to consent to defer empiric treatment and abstain from sex of any kind (oral, anal or vaginal) until their clinical NAAT results for CT and GC are available. Consent will be obtained by asking the individual to read and sign the appropriate consent form. The ICF form will be signed prior to performing any study procedures.
- Demographic information will be obtained by interview of the subject.
- A subset of eligibility criteria will be reviewed with the subject.
- Subject contact information for follow-up and study visit reminders will be collected.
- Subjects will be scheduled to return to clinic for Visit 1 when CT and GC NAAT test results are expected (i.e., based on the local lab test turnaround time).

AFTER VISIT 0 ENDS AND PRIOR TO VISIT 1

- Study staff will follow up on the results of clinical labs.
- Subjects who test positive for rectal CT and negative for GC will return for the Enrollment Visit, which is scheduled at the end of the Screening Visit.
- Subjects whose clinical NAAT tests return with any ineligible results (i.e., CT positive, GC positive; CT negative, GC negative; CT negative, GC positive) will be informed that they are no longer eligible. Study staff will arrange for and ensure appropriate treatment based on standard clinical practices at each site.

7.2 Visit 1 – Screening and Enrollment/Baseline Visit, Day 1

- Sites will follow their site-specific instructions for approaching and pre-screening MSM for this trial. Two types of subjects will be recruited:
 - High risk MSM who consented to deferring empiric treatment at the screening visit and NAAT test results return positive for CT and negative for GC.

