5. SAMPLE SIZE CONSIDERATIONS

The sample size and power calculations were derived for a two-staged group sequential design with one unblinded interim analysis of the primary outcome halfway through the trial and the final analysis after the trial has been completed.

O'Brien-Fleming boundaries will be used for the interim and final analyses to control the overall Type I error of the trial. The choice of O'Brien-Fleming is motivated by the desire to stop the trial early only if the interim difference in cure rates between treatment groups is large, and to continue in the presence of a moderate or small interim difference. For the calculations, it was assumed that the interim analysis will occur when 50% of the planned number of primary analysis-eligible subjects have been enrolled and followed through Day 29.

The sample size for the study was updated from the original target due to logistical and feasibility reasons. The enrollment target is 274 subjects. Based on previous prospective studies of MSM recruited from the PHSKC STD clinic [reference 10-13 in protocol], it is anticipated that at least 90% of enrolled subjects will be eligible for the primary analysis population; therefore, it is expected that 274 enrollments will lead to approximately 246 subjects eligible for the primary analysis.

Previously reported cure proportions have generally ranged 95-100% for doxycycline and 74-92% for azithromycin [reference 14-20 in protocol]. The 246 primary-analysis-eligible subjects along with the O'Brien Fleming boundaries will provide 75-80% power to detect a 10% difference in cure rates between treatments using conservative estimates of treatment-specific cure rates based on the literature (~95% cure rate for doxycycline and ~85% cure rate for azithromycin). The study will have more than 80% power to detect a 10% difference across a range of cure rates of doxycycline and azithromycin consistent with rates calculated in a meta-analysis of the efficacy of azithromycin and doxycycline for the treatment of rectal chlamydia infection [reference 9 in protocol]. See [Table 3](#) below for power estimates.

Table 3: Power available to detect a 10% difference in cure proportions between treatments detectable with total sample size of N = 246 and interim analysis at N = 123

Cure Proportion		Power
Doxycycline	Azithromycin	
95%	85%	75%
96%	86%	79%
97%	87%	83%
98%	88%	87%
99%	89%	92%

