6.5. Missing Data

Subjects with unknown microbiologic cure status will be excluded from the CC and PP population. For ITT analyses, such subjects will be included with their cure status imputed as microbiological failures.

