8. EFFICACY EVALUATION

8.1. Interim Analysis

The primary efficacy endpoint for the interim analysis is the proportion of subjects with microbiologic cure in each study arm at Day 29. See Section 3.3.1 for the definition of microbiologic cure.

A test of hypothesis comparing the proportion of subjects with microbiologic cure at Visit 3 (Day 29) in each treatment group will be conducted in the CC population. The null hypothesis for the comparison is that there is no difference in proportions between treatment arms, with a two-sided alternative that considers the possibility of a difference in either direction. The test will be conducted using a Pearson Chi-Square test at the 5% two-sided significance level. The resulting test statistic will be compared to the O'Brien Fleming bound calculated in the study's sample size calculations. At the interim point the bound is |2.79651|, thus if the test statistic is either greater than 2.79651 (Group A cure rate is higher than Group B cure rate) or less than -2.79651 (Group B cure rate is higher than Group A cure rate), then the resulting action should be to stop the trial. Otherwise, the resulting action should be to continue on to the full sample size.

The proposed summaries to be generated for the interim analysis were approved by the DSMB at the organizational meeting on 30MAY2018 and they are copied in this SAP. The summaries will be semi-blinded, where the treatment group labels will be "Group A" and "Group B". Table 11 will summarize eligibilities for and reasons for exclusion from the CC population for all randomized subjects. Table 12 will present the microbiological cure rates with confidence intervals by treatment group. Also included is the test statistic and the O'Brien Fleming critical value.

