8.2. Final Analysis

8.2.1. Primary Efficacy Analysis

The primary efficacy endpoint for the final analysis is the proportion of subjects with microbiologic cure in each study arm at Day 29. See Section 3.3.1 for the definition of microbiologic cure.

A test of hypothesis comparing the proportion of subject with microbiologic cure at Visit 3 (Day 29), will be conducted in the CC population. The null hypothesis for the comparison is that there is no difference in proportions between treatment arms, with a two-sided alternative that considers the possibility of a difference in either direction. The test will be conducted using a Pearson Chi-Square test at the 5% two-sided significance level. The number of subjects, the proportion of subjects with microbiologic cure, and the 95% Wilson confidence interval for the proportion of subjects with microbiologic cure will be presented overall and by treatment group. In addition, the difference in proportions between the Azithromycin group and the Doxycycline group and 95% Wilson confidence intervals will be presented.

The test statistic will be compared to the O'Brien Fleming bound calculated in the study's sample size calculations to determine significance. At the final analysis the bound is |1.97743|, thus if the test statistic is either greater than 1.97743 (doxycycline cure rate is higher than azithromycin cure rate) or less than -1.97743 (azithromycin cure rate is higher than doxycycline cure rate), then the resulting interpretation is that the cure rates are significantly different between arms. Otherwise, the resulting interpretation is that the cure rates are not significantly different between arms.

The above analyses, apart from the O'Brien Fleming bound comparisons will be repeated in the ITT and PP analysis populations.

See [Table 13](#), [Table 14](#), and [Table 15](#). See Section 6.1 for pseudocode to fit the above analyses. Individual efficacy response data is presented in [Listing 6](#).

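### The supportive ITT analysis codes men with a negative Visit 1 swab as cured, so its estimate shrinks slightly and does not isolate the effect of missing outcomes

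*SAP*

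**What the plan says.** **Who enters ITT.** Protocol 10.4.1.2 defines ITT as all randomized subjects. SAP 6.3.2.1 adds that membership holds "regardless of whether they received study treatment, had a positive baseline rectal CT NAAT result, or were compliant with the administration procedures or schedule".

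**How a man qualifies.** The inclusion criterion is "Untreated rectal CT diagnosed by a positive NAAT result" (Protocol 5.1), confirmed from a laboratory report or medical record. A separate study swab is taken at Visit 1, the visit at which he is randomized and takes his first dose (Protocol 4 and 7.2). Nothing in the documents makes randomization wait for that swab's result.

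**How cure is coded.** SAP 3.3.1, Table 1, uses only the Visit 2 and Visit 3 NAAT results. Every row with a negative Visit 3 result is a cure; the baseline result is not an input. Under SAP 6.3.2.4, a chlamydia-active antibiotic before the visit makes a man a failure in ITT and CC. For unknown status, SAP 6.5 says: "For ITT analyses, such subjects will be included with their cure status imputed as microbiological failures".

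**Where the formal test sits.** The CC and PP populations both require a positive baseline NAAT (SAP 6.3.2.2 and 6.3.2.3). The interim and final O'Brien-Fleming comparisons are made in CC only. SAP 8.2.1 repeats the other primary analyses in ITT and PP. SAP Table 7 has a row for men without a positive baseline result, so the plan foresees them.

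**The concern.** A man who is negative at Visit 1 and still negative at Day 29 counts as a success in whichever arm he was assigned to. If he had no infection when dosed, he carries no information about which drug works better. He raises both cure rates and pulls the difference toward zero.

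This matters because of what ITT is used for. The primary analysis is a complete-case analysis, and a reader will look to ITT to see how far missing outcomes could move the result. It is the only planned efficacy analysis that keeps men with unknown status. Protocol 10.4.4.1 promised sensitivity analyses for missing data with details in the SAP, but SAP 12 plans no additional analyses. In moving from CC to ITT, two things change at once: unknown outcomes become failures, and baseline-negative men come in, mostly as cures. The ITT estimate alone does not show the effect of the first change.

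**Working it through.** **Inputs.**
- Planned cure: "95% cure rate for doxycycline and ~85% cure rate for azithromycin" (SAP 5). SAP Table 3 also has a 97% vs 87% row. Both are 10-point differences.
- 274 enrolled, 1:1, so 137 per arm; 246 expected in CC, so 123 per arm; at least 90% expected to be CC-eligible (SAP 5).
- Bounds 2.79651 (interim) and 1.97743 (final) (SAP 8.1 and 8.2.1).
- Baseline-negative share f and unknown-outcome share m: neither is given. Assumed f = 3–5% and m = 5%, equal in both arms.

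**1. The plan's own figures.** A two-look calculation with these bounds and 123 per arm gives an overall type I error of 0.0500. Power at 95% vs 85% is 0.752 (unpooled variance) or 0.743 (pooled), against the stated 75%. Enrolment: 246 / 0.90 = 273.3, rounded up to 274. Both reproduce.

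**2. Dilution formula.** If baseline-negative men are negative at Day 29 and unknowns are failures, the ITT cure rate in an arm with true cure p is (1−m) × [(1−f) × p + f]. The term in f is the same in both arms and cancels, so the ITT difference is (1−m)(1−f) × 10 points. Restricted to baseline-positive men it is (1−m) × 10 points.

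At 97% vs 87% with m = 5%:
- f = 3%: 0.9224 − 0.8302 = 9.2 points
- f = 5%: 0.9229 − 0.8327 = 9.0 points
- baseline-positive men only: 0.95 × 10 = 9.5 points

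The loss due to baseline-negative men is therefore 0.3–0.5 point.

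**3. Cap from the plan.** If about 90% of men reach CC, (1−m)(1−f) is about 0.90, so the combined loss is about 1 point of 10. Using the planned counts, 10 × 123/137 = 8.98 points.

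**4. Why the ITT estimate cannot separate the two causes.** Take the 274 − 246 = 28 planned non-CC men, 14 per arm, with b baseline-negative and 14 − b unknown in each arm. The ITT cure rate is (123p + b)/137, so the difference is 12.3/137 whatever b is. Among baseline-positive men it is 12.3/(137 − b).

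| Split per arm | ITT difference | Baseline-positive, unknown = failure | ITT power at 95% vs 85% |
|---|---|---|---|
| 14 unknown | 8.98 | 8.98 | 0.471 |
| 7 and 7 | 8.98 | 9.46 | 0.570 |
| 14 baseline-negative | 8.98 | 10.0 | 0.741 |

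The ITT difference is identical in all three rows; the restricted estimate distinguishes them. (Power is for a two-sided 5% test with 137 per arm.)

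**5. Power.** At 95% vs 85%, f = 5% and no unknowns, ITT power is 0.768 with these men and 0.770 without them. The issue is interpretation, not power.

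**The case against.** The strongest case against the point is that full ITT is meant to include everyone randomized. The SAP names baseline-negative men explicitly, so this is a stated choice that agrees with the protocol. Every formal decision is made in CC, which excludes them. The effect is a fraction of a point, and counting unknowns as failures costs ITT far more power (0.471 against 0.741 for the same 28 men). The proposed extra row keeps that imputation. All of this stands, and it keeps the point small.

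Some stronger readings are tempting, but the documents do not support them:

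- *The planned outputs cannot show why ITT and CC differ.* They can in part. Table 7 counts, by arm, men without a positive baseline result and, separately, men without Day 29 data. Listing 1 gives each man's exclusion reason, and Listing 6 his Visit 2 and Visit 3 results. What is missing is a cure estimate without the baseline-negative men.
- *The dilution could be much larger.* A 10% share with 5% unknown would leave at most 0.95 × 0.90 = 85.5% in CC, below the plan's 90%.
- *These men were uninfected.* That is an inference. Each had an earlier positive NAAT. A negative Visit 1 swab may mean clearance, an earlier false positive, or a false negative on a swab that may be self-collected. Infected men among them would make the dilution smaller than the formula gives.
- *The qualifying test is typically a month old.* For high-risk men, Day −30 is the outer limit; Protocol 7.1 schedules Visit 1 by laboratory turnaround. For men found by routine screening, no limit is stated.
- *The two rules offset each other.* They do so for the cure rates only. Both shrink the difference.

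The last non-evaluable category in SAP 3.3.1 could be read to cover these men. They would then be ITT failures, and the difference would shrink by the same factor.

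**Conclusion.** The point holds as a limited weakness of a supportive analysis. Under SAP 6.3.2.1 and Table 1, a baseline-negative man with a negative Day 29 swab and no chlamydia-active antibiotic is an ITT cure, and no rule recodes him. The ITT difference falls by the factor (1−f): from 9.5 to 9.2–9.0 points at an assumed 3–5% baseline-negative and 5% unknown, with a combined loss from both groups of about 1 point of 10 under the plan's own 90% expectation. These figures assume that both groups are spread evenly over the arms and that the baseline-negative men had no infection to treat.

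A reader might infer that the trial's conclusion is at risk. It is not: the primary test excludes these men, and the dilution runs toward no difference, so it cannot create a false finding of superiority. What is lost is a clean reading of how missing outcomes affect the result.

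**What to change.** Keep full ITT in Tables 14 and 17 and in the ITT subgroup tables, as the protocol specifies. Add to SAP 6.3.2 a supportive modified ITT population: all randomized men with a positive Visit 1 rectal CT NAAT, analysed as randomized, with unknown Day 29 (or Day 15) status imputed as failure. Report it as an additional row in those tables.

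The restriction respects the randomized comparison, because the swab is taken before dosing and laboratory staff are blinded (Protocol 5.3.2 and 7.2). The step from CC to the new row then mainly shows missing outcomes, and the step from the new row to full ITT shows baseline-negative men. The first step would still include any men who failed another eligibility criterion (counted in Table 7) or received the wrong treatment (Listing 2).

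The cost is SAP wording, one population flag and one more set of rows. No new data are needed.

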6.3.2.2. Complete Case (CC) Population

The Complete Case (CC) population includes all randomized subjects who meet all inclusion/exclusion criteria at enrollment, have a positive baseline rectal CT NAAT result, and have post-baseline microbiologic data available. For analyses at Day 15, microbiologic data must be available from the Day 15 visit. Likewise, for analyses at Day 29, microbiological data must be available from the Day 29 visit.

The CC population will be the primary efficacy analyses population.

6.3.2.3. Per-Protocol (PP) Population

The Per-Protocol (PP) Population includes all randomized subjects who meet all inclusion/exclusion criteria at enrollment, have a positive baseline rectal CT NAAT result, have post-baseline microbiologic data available, sufficiently adhere to the assigned study drug regimen (defined in Section 3.3.4), and do not experience either of the following after enrollment and before a particular visit (Day 15 for analyses at Day 15, and Day 29 for analyses at Day 29):

- Receipt of an antibiotic active against CT
- Have condomless receptive anal sex

For analyses at Day 15, microbiologic data must be available from the Day 15 visit. Likewise, for analyses at Day 29, microbiologic data must be available from the Day 29 visit.

6.3.2.4. Considerations for Analysis Populations

In the unlikely event of an error in randomization or study drug administration, subjects will be grouped by the formulation they actually received in Safety, CC, and PP analyses but will be grouped by their intended randomized assignment in ITT analyses.

Before unblinding, a blinded case review committee will review subjects with a reported concomitant infection/disease/procedure that may interfere with study drug, use of concomitant medications or products that may interfere with study drug, significant protocol deviations, treatment adherence, and other events that may impact study drug effectiveness or study analyses. On a case-by-case basis, the case review committee will determine if each subject will be included in the PP population, if and when a subject should be censored or removed from PP analyses, and/or any other analytical requirements for the subject. The committee will be blinded to both treatment group and outcome status for each case.

Subjects who receive treatment with an antibiotic active against CT for any reason before a particular post-baseline visit (Day 15 for analyses at Day 15, and Day 29 for analyses at Day 29) will be included in ITT and CC analyses as treatment failures and reviewed by the blinded case committee for inclusion in PP analyses.

